5.3 Informed Consent Procedures

Informed consent will be obtained from all participants. Potential participants will be approached by study personnel (recruiter or other study team member). This will either be done via mailed letter, in person or by phone. It is also possible that a potential participant will see one of our flyers or other marketing and call the recruiter. If recruited in person, the recruiter will ascertain eligibility and do informed consent in a private office. These particular participants will be identified by clinical study personnel or other approved means.

It will be explained to participants that if they choose not to participate they will receive the services that they would ordinarily receive and that is there is no penalty for not participating and that the study is entirely voluntary and that they are free to withdraw from the study at any time. All personnel involved in the informed consent process will be trained by the PI to ensure that the process is explained properly and that there is no undue coercion. The voluntary nature of the study will be emphasized and potential participants will be able to take home the consent document to read at their leisure if they prefer.

Primary recruitment will be through TBI-relevant clinics at both Bay Pines and Tampa VAs. Both facilities have active PNS clinics (Polytrauma Network Sites), Post-Deployment, PTSD and other clinics with patients identified to have a history of mild TBI. The recruiter and PI/Site PI and co-investigators will identify potential participants through their regular contact with patients. When a clinician determines that a patient is eligible (based on study inclusion/exclusion criteria), the clinician will either approach the patient to discuss his/her interest in research, or will refer the patient to a member of the research team. The recruiter, or other co-investigators, will approach potential participants, inform them of the study, and verify their eligibility. If potential participants are interested, the recruiter will obtain informed consent and HIPAA authorization. Or, if interested participants reside a distance away from the VA and would like to participate in the study the informed consent process will be done over the telephone.

5.4 Inclusion/Exclusion Criteria

Inclusion/Exclusion Criteria: To be eligible for the study, participants will be 18 or older with a history of mild TBI (DoD/VA criteria⁶⁶ as determined by trained, experienced staff via interview and medical record review via comprehensive evaluation process within PNS Clinic⁶⁵) with current symptoms complaints (operationally defined as at least two symptoms on the NSI endorsed at the 'moderate' level or a total score on the NSI greater than 25. At least 93.5 percent of a sample of over 50,000 individuals with mild TBI within VA reported at least two NSI symptoms at a moderate level of severity or higher.⁶⁷ In addition, eligible participants must speak and read English, not have a history of moderate to severe TBI, not have a self-reported diagnosis of psychosis or be actively suicidal. Finally, potential subjects who report prior experience with Concussion Coach will also be excluded. We will attempt to recruit women and minorities to the extent possible. Our experience suggests that approximately 4% female and 30% ethnic minority will likely participate; they agree to participate in research at about the same rate as male and non-minority participants. Subjects who meet the inclusion/exclusion criteria and who agree to participate in the research study will sign an informed consent.

5.5 Study Evaluations

Table 1 outlines quantitative measures we propose to use. Examination of potential mediator and moderator variables will allow us to determine who is most likely to benefit from the intervention (e.g., people with limited social support, people who are less 'tech savvy') and qualify our findings. Justification for each of these included variables is contained in the description of each measure below the table.

Table 1. Study Measures

Construct	Tool	Timepoint
Primary Outcomes		
PCS	Neurobehavioral Symptom Inventory (NSI)	Baseline, up to 1 year later
Symptom Exaggeration	mBias	Baseline, up to 1 year later
Psychological Distress	Brief Symptom Inventory (BSI) PCL-5 Strong Star (PCL)	Baseline, up to 1 year later

Time Spent on Concussion Coach in total and on various components	Concussion Coach download	Duration of study i.e. a 3 month period for use of APP
PCS	NSI from Concussion Coach download (could be multiple NSIs depending on subject)	Duration of study i.e. a 3 month period for use of APP
Barriers and Facilitators of Concussion Coach use and effectiveness	Concussion Coach Interview Follow-Up Data Form	Up to 1 year later for Follow-Up Form. Interview date is an undetermined time after the final study visit.
Potential Mediators		
Perceptions and Knowledge of Illness	TBI Education Satisfaction, Knowledge, and Attributions	Baseline, up to 1 year later
Self-Efficacy	Self Efficacy for Symptom Management Scale (SEsx)	Baseline, up to 1 year later
Potential Moderators		
Social Support	Social Support Questionnaire – Short Form (SSQSR)	Baseline, up to 1 year later
Comfort with Technology	eHealth Literacy Scale (eHEALS)	Baseline, up to 1 year later
Use of Apps during study period	Follow-Up Data Form	Up to 1 year after Baseline
Mental Health Treatment during study period	Follow-Up Data Form	Up to 1 year after Baseline
Demographics, Health and Disability Status		
Age, gender, diagnosis, comorbidities, other injuries.	Medical Record: Participant Information Form Enrollment Participant Information Form	Baseline

Primary Outcome Measures:

- Neurobehavioral Symptom Inventory (NSI) is a 22-item questionnaire developed to evaluate post-concussion symptoms following mild TBI.⁵² It is used throughout the VA system of care to assess complaints associated with identified concussion. Patients are asked to rate each symptom on a scale of 0-4 (none, mild, moderate, severe, and very severe) with three different types of symptoms: affective/psychological/stress, somatic/physical, and cognitive reflecting three factors. The total score will be used in primary analyses. It is our primary outcome of interest because the civilian literature on interventions for mild TBI has focused (and found effects) on symptom-based measures.^{41 53} Our own pilot data suggests that educational interventions have a significant impact on this measure.
- mBIAS is a 5-item measure of atypical symptoms. It is associated with symptom exaggeration following mild TBI (Cooper et al., 2011).
- Brief Symptom Inventory 18 (BSI 18) is a self-report measure with 18 items designed to measure psychological distress. It can be completed in approximately 4 minutes and is well-suited for helping measure symptom change due to treatment. It has good psychometric properties and has been used in the population of interest. It measures three primary dimensions: Somatization, Depression, and Anxiety, as well as a Global Severity Index (GSI). The GSI will be used in primary analyses as a measure of overall psychological distress. The Posttraumatic Stress Disorder Checklist (PCL-5) is a 20-item, self-rating scale that provides a quick and accurate measure of PTSD symptoms. Each item corresponds to current diagnostic criteria of PTSD, and each symptom is rated in terms of frequency and severity (Weathers, Huska, & Keane, 1991).Participant use of Concussion Coach will be collected electronically, including total time spent using the app as well as each component.
- Concussion Coach Interview (Tampa VA, unpublished). We have developed an interview that combines open-ended questions about use of the Concussion Coach with rating scales to assess satisfaction with the TBI app. Interviews will be conducted with a purposive sample of 10% of Concussion Coach users at study end to evaluate their satisfaction with Concussion Coach, ease of use, barriers and facilitators to use of Concussion Coach, behavioral intention to use Concussion Coach in the future and recommendations for improving it. We will use purposive sampling for participation in these interviews. We will solicit interviews from 10% of those who improved on PCS using Concussion Coach and 10% who did not improve or became worse. In addition to qualitative questions about barriers and facilitators, interview questions will include quantitative assessment of satisfaction (e.g., rating scales of satisfaction). Interviews will be conducted by experienced trained interviewers (e.g., [name]) and will be audio recorded. Participants will already be consented, so the interviewer will identify and briefly recap the project, and then ask permission for audio tape recording. Interviews will be conducted by phone or in person based on participant convenience. The interviewer will use standard communication techniques to stimulate discussion such as generic prompts (e.g. tell me more), summarizing statements, silence, and eve contact, if conducted in person, If the respondent exhibits adverse reactions, such as shame, during the course of the interview, every effort will be made to encourage him or her and they will be reminded of their rights as participants.
- Follow-Up Data Form Potential Mediators:
- TBI Education Satisfaction, Knowledge, and Attributions Questionnaire is a 24 item modified version of the Brief Illness Perceptions Scale,⁵⁴ which assesses TBI education, knowledge, and attributions related to PCS. This measure is included due to the well known impact that

- symptom attributions can have on outcomes following mild TBI ⁵⁵⁻⁵⁷ and to explore the relationship between outcomes and prior exposure and satisfaction with the VA's existing TBI education.
- Self Efficacy for Symptom Management Scale (SEsx) is a measure of confidence or perceived self-efficacy for managing chronic conditions. Perceived self-efficacy has been shown to influence a broad range of health-related and rehabilitation outcomes and may be particularly relevant in examining the effects of neuropsychological rehabilitation. Previous research has demonstrated an empirical relationship between generalized self-efficacy and outcomes after TBI.⁵⁸

Potential Moderators:

- Social Support Questionnaire Short Form (SSQSR) ^{59 60} is a 12-item questionnaire that measures both availability and satisfaction with social support. Social support is known to be associated with outcomes from TBI.^{61 62}
- An adapted eHEALS, 10-item measure of eHealth literacy was developed to measure consumers' knowledge, comfort, and perceived skills at finding, evaluating, and applying electronic health information to health problems. Based on responses of 664 participants aged 13 to 21 internal consistency reliability was found to be .88. Test-retest reliability from baseline to 6-month follow-up (r = .68 to .40). Principal components analysis produced a single factor solution (56% of variance).⁶³

Demographics, Health and Disability Status:

- The Participant Information Form gathers pertinent demographic data.
- Enrollment Participant Information Form

Individual interviews (see Appendix for script) will be conducted with 10% of the Concussion Coach users at study end to evaluate their satisfaction with Concussion Coach, ease of use, their perception and satisfaction with other TBI-related education they have received within the VA to date, barriers and facilitators to use of Concussion Coach, and behavioral intention to use Concussion Coach in the future. This 10% sample will not be random – rather, we will solicit interviews from those who improved on PCS using Concussion Coach, those who did not get better or became worse, and those who did not use the App during the study period or used it infrequently. In addition to qualitative questions about barriers and facilitators, interview questions will include quantitative assessment of satisfaction (e.g., rating scales of satisfaction). Interviews will be conducted by experienced trained interviewers (i.e., [name]) and will be audio recorded. Participants will already be consented in person or over the telephone, so the interviewer will identify and briefly recap the project, and then again ask permission for audio tape recording. Interviews will be conducted by phone or in person based on participant convenience. The interviewer will use standard communication techniques to stimulate discussion such as generic prompts (e.g., tell me more), summarizing statements, silence, and eye contact, if conducted in person. If the respondent exhibits adverse reactions, such as shame, during the interview, every effort will be made to encourage him or her and they will be reminded of their rights as participants.

5.6 Data Analysis

[figure not shown]
Sample Size Justification: Below is a diagram of the expected subject recruitment and attrition (see Figure 2). Our recruitment estimates are based on our experience with prior trials (e.g., a recent pilot study of a web based intervention successfully recruited over 90% of potential participants) and our emphasis in the budget of recruitment personnel who will be embedded in our clinics. We conservatively estimate that 60% of potential participants will agree to participate and be successfully enrolled in the study. Our attrition estimate of 20% is based on our experience with an internet self-help intervention study, during which drop out was less than 20%. This was accomplished through continued outreach by the recruiter via letter and calls. Based on these conservative numbers and a recruiting period of 33 months we expect a minimum N=388 participants in the study [(20 newly identified participants per month over 33 months + 150 existing) *60% participation* (1-20% attrition)]. This is a conservative estimate

because we have excluded the existing 1,332 potential participants living in our area (national dataset) to whom we will mail letters.

For each regression model proposed for H1&2, results of sample size calculation using the application PASS v11 (Hintze, 2011) show that a much smaller N=148 (or N=194) achieves 80% (or 90%) power to detect an additional R-Squared of 0.05 (proportion of explained variation in the outcome) attributed to 2 independent variables (TBI Coach plus an interaction) using an F-Test with alpha of 0.05. This assumed the variables tested are adjusted for 10 independent variables with an R-Squared of 0.20.

We note that of all statistical models proposed in this study, the mediation model has the most stringent sample size requirement. With conservative total N=388, we expect to have greater than .80 power to detect a small to medium effect size of the mediated effect at alpha = 0.05. The two regression coefficients (beta1 & beta2) that jointly capture the mediated effects are critical in the power calculation for a mediation

Figure 2. Expected Total Recruitment

model. Using the parameter values of 0.14, 0.39, and 0.59, corresponding to Cohen's criteria68 for small (2% of the variance), medium (13% of the variance), and large (26% of the variance) effect sizes, respectively, Fritz and MacKinnon (2007) conducted empirical estimates of sample

sizes needed for .8 power at 95% confidence level. Their results showed that when bias-corrected bootstrap is used, N=462 is adequate to detect small effect size for each of alpha and beta while N=377 is adequate to detect small/medium effect size combination for both alpha and beta.69 Conservatively we expect to recruit N=388. We calculated directly the power for testing mediation effect based on Sobel's test (Sobel, 1982) using the R package 'power Mediation'. By specifying Cohen's small ES for each coefficient in the indirect pathway (beta1 = beta2 = 0.14) and with the following assumptions: both the predictor and the mediator have S.D. of 0.5 while the square of the correlation between both equal 0.3; and S.D. of the random error term is 0.2; the expected N=388 will provide 0.82 power to detect the small mediation effect size.

Sample Size for Qualitative Research Questions: In qualitative research, sample size relies on the quality and richness of information obtained. A chieving conceptual saturation is the goal of qualitative research and is not dependent on sample size but on the ability of the data to support interpretations, i.e. saturation. For this aim, we project saturation will occur within the first twelve interviews; meta-themes will present in six interviews. Thus we will recruit 10% of Veterans to provide adequate data to represent sub-groups that may emerge from the sample and allow for an adequate sub-sample sizes; allowing for some attrition. For example, we expect low volume and high volume users; those who intend to have continued use and those who may not. This will also allow sampling groups for analysis by socio-demographics such as gender and race. We have budgeted to recruit 10% of Veteran participants to conduct the proposed interviews.

Data Analysis:

Data from the Concussion Coach application will be electronically sent to the USF server. It will be de-identified (but matched to a study number that will identify the individual to the study coordinator who will need it for follow-up). It will be periodically emailed to study personnel at the Tampa VA.

Data from paper questionnaires will be obtained from the recruiter and study personnel and maintained by the study coordinator. Again, study numbers will be used to identify participants.

All data will be combined into a study database. The integrity of the database will be managed by our database manager. Analyses will be conducted by the statistician ([name]) and the PI ([name]).

Data Analysis Plan: An intention-to-treat (ITT) analysis will be performed, that is analysis will be based on the groups to which participants are randomized regardless of whether they receive or adhere to the assigned intervention. This will allow us to test the effects of assigning TBI Coach in practice, separate from assessing effects of adherence and/or loss to follow-up. Those who are lost to follow-up and therefore are missing outcome measures (T2 assessments) will be included in separate comparison analyses that utilize multiple imputations of the missing data.

For each primary outcome and other measures consisting of multiple items, a summation score will be produced for each subject. Summary of each variable by intervention group will be cross-tabulated. The time spent on TBI Coach and its specific components on the average will also be tabulated. All primary outcomes will be analyzed as continuous variables. Exploratory bivariate plots will be used to investigate possible nonlinear relationships between baseline/covariates and each follow up outcome variable. In separate statistical models proposed, we will control for demographics and other covariates including the baseline values of the outcome under investigation. Where appropriate, nonlinear regression model will be utilized (e.g., generalized additive model).

Hypothesis 1 (Primary Hypothesis): Patients randomized to receive TBI Coach for 3 months will have (a) lower post-concussive symptom severity and (b) lower psychological distress, compared to patients randomized to a no intervention control group, after adjusting for baseline severity and other potential confounders.

Analysis: The two intervention groups (TBI Coach = 1; Control = 0) will be compared on each outcome (a) and (b) in separate regression models that include the group variable and control for the outcome at baseline and other potential confounders. A significant positive estimated coefficient of the group variable will indicate positive TBI Coach's effects on the outcome, with the standardized value of the coefficient as the standardized effect size.

Hypothesis 2: The effects of TBI Coach on PCS (and psychological distress) will be greater for Veterans who have (a) greater comfort with technology at baseline than for those who are less comfortable; (b) greater social support at baseline than for those with less social support.

Analysis: Two separate tests of moderated effects of TBI Coach will be performed with respect to each outcome. Each regression model in H1 (one per outcome) will be extended by adding a 2-way interaction term (between intervention and (a) eHealth Literacy Scale and (b) Social Support score; one at a time (i.e. two different moderation models per outcome). A significant coefficient of an interaction term will indicate presence of interactive effects. A co-plot using model fitted values will also be produced to further investigate the nature of any significant interaction.

Hypothesis 3: If TBI Coach improves Veterans' (a) knowledge about TBI and attribution of symptoms and/or (b) self-efficacy in coping with symptoms, Veterans will have less PCS and Psychological Distress.

Analysis: Single-mediator models⁷³ will test the indirect effects of the group variable (TBI Coach) on each outcome (separately) with respect to mediating variables: (a) knowledge and attribution, and (b) self-efficacy. Preliminary regression analyses will test whether (1) TBI Coach substantially changes the mediating variable, and (2) the mediating variable changes the outcome. Next, we will proceed to a full mediation model with simultaneous estimation of both direct and indirect effects of TBI Coach on the outcome. The mediated effect will be estimated as a product of the two path coefficients alpha and beta in the indirect pathway. The distribution of the product of coefficients is non-normal and this has implications for statistical inference as well as power calculation (see section on sample size justification). Therefore, the analysis will

be performed using the Mplus statistical application which offers alternatives that do not require the regular assumption of symmetric, normal distributions for parameter estimates. Bayesian estimation method with diffuse priors will be used with appropriate posterior simulation schemes based in Markov Chain Monte Carlo (MCMC) methods. One advantage of the MCMC estimation process is that it provides accurate tests of mediated effects for small samples; e.g. by simply taking the product of the two coefficients alpha and beta for every draw and compute its standard deviation across all draws to obtain standard errors of mediated effect. Also, unlike the normal-based ML confidence interval, inference will rely on Bayesian credibility interval based on the percentiles of the posterior, which easily allows for a strongly skewed distribution alphabeta product⁷⁴

Hypothesis 4: More time spent on (a) TBI Coach use, and (b) specific interactive components of TBI Coach (i.e., the "tools" section) will be associated with lower PCS symptom severity after adjusting for baseline PCS values and potential confounders.

Analysis: A regression model of PCS will be performed on the TBI Coach sample only, separately for (a) TBI coach use, and (b) each interactive component as the main predictor. First the PCS baseline score, demographics and other potential confounders will be included in the base model. Then a full model with addition of the time score for one TBI Coach aspect at a time will be fitted. Appropriate transformation (e.g. log) of all time variables will be done as suggested by their general distribution; a significant negative coefficient of the time variable will confirm a negative association between time spent on that component and symptom severity. Standardized coefficient estimates as well as R-sq estimates will be obtained so that all TBI Coach aspect-specific models can be compared on the relative strengths of the aspect-outcome relationships.

As an extension, secondary analysis will be performed on the TBI Coach components that show strong relationship in the expected direction. Each time spent (as a dependent variable) will be regressed on the predictors in the base model to identify both positive and negative contributory factors to the specific component usage.

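### The mediation power figures belong to Sobel's test and the bias-corrected bootstrap, not to the percentile credibility interval that decides Hypothesis 3

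*Combined protocol and SAP*

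**What the plan says.** All of this is in section 5.6, Data Analysis, of the combined protocol and SAP.

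- **Sample Size Justification, the claim.** The mediation model is described as the most demanding of all the models, and at N=388 "we expect to have greater than .80 power to detect a small to medium effect size of the mediated effect at alpha = 0.05".
- **First support.** Published simulation results are cited: "when bias-corrected bootstrap is used, N=462 is adequate to detect small effect size for each of alpha and beta", and N=377 for a small/medium combination. Path values of 0.14, 0.39 and 0.59 stand for small (2% of the variance), medium (13%) and large (26%).
- **Second support.** "We calculated directly the power for testing mediation effect based on Sobel's test", with both coefficients 0.14, predictor and mediator SD 0.5, squared correlation 0.3, error SD 0.2 and N=388. The result is 0.82, described as power for a small mediated effect.
- **Hypothesis 3 analysis.** "The distribution of the product of coefficients is non-normal and this has implications for statistical inference as well as power calculation", with a pointer back to the sample size section. The model is fitted by MCMC with diffuse priors, and "inference will rely on Bayesian credibility interval based on the percentiles of the posterior". The plan sets this against the normal-based interval, which it does not want to use.

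**The concern.** The analysis text sets normal-theory inference for the product of paths aside and sends the reader to the sample size section for what non-normality means for power. That section then computes power with the normal-theory test, and borrows sample sizes from a third procedure, the bias-corrected bootstrap, that the analysis does not use either.

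The two borrowed tests err in opposite directions, so a reader cannot apply one mental correction. The plan names mediation as its most demanding model, so these figures carry part of the case for N=388. A null Hypothesis 3 result, read against a stated 0.82 for a small mediated effect, would look like stronger evidence against small mediation than the planned analysis can give.

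**Working it through.** **Inputs.** All are from section 5.6 unless marked as assumed: n=388; b1=b2=0.14; SD of predictor sx=0.5; SD of mediator sm=0.5; squared correlation r2=0.3; error SD se=0.2; standardised paths 0.14 and 0.39; cited N=462 and 377. Assumed: two-sided 5%; a 95% interval that must exclude zero; flat priors; no multiplicity adjustment. For the standardised cases also assumed: unit-variance predictor and residuals, no direct effect, no covariates.

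**1. The plan's own figures reproduce.**

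N: (20×33 + 150) × 0.60 × 0.80 = 810 × 0.48 = 388.8.

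Sobel:
- z1 = b1·√n·sx / (sm·√(1−r2)) = 0.14 × 19.698 × 0.5 / (0.5 × 0.8367) = 3.296
- z2 = b2·√n·sm·√(1−r2) / se = 0.14 × 19.698 × 0.5 × 0.8367 / 0.2 = 5.768
- combined z = 1/√(1/z1² + 1/z2²) = 2.862
- power = Φ(2.862 − 1.960) = 0.816, the printed 0.82. A one-sided test would give 0.888, so the printed figure is two-sided.

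Bias-corrected interval: 0.80 at N=462 for 0.14/0.14, and 0.80 at N=377 for 0.14/0.39. Both cited sample sizes reproduce.

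**2. The planned rule.** With flat priors the posterior probability that the product is negative is p = pa(1−pb) + (1−pa)pb, where pa = Φ(−estimate/SE) for the first path and pb likewise for the second. The 95% percentile interval excludes zero when p < 0.025 or p > 0.975. Averaging over the sampling distribution of the two estimates, by numerical integration and by simulation of the two regressions, gives:

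| Case | Figure in plan | Planned interval |
|---|---|---|
| Printed Sobel inputs, N=388 | 0.82 (Sobel) | 0.91 |
| 0.14/0.14, N=462 | .8 (bias-corrected) | 0.70–0.71 |
| 0.14/0.39, N=377 | .8 (bias-corrected) | 0.78 |
| 0.14/0.39, N=388 | greater than .80, if this is the pair meant | 0.78–0.79 |
| 0.14/0.14, N=388 | 0.82, if small means 0.14 standardised | 0.58–0.60 |

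For 0.14/0.14 the planned interval needs about N=540 to reach 0.80. In the first row, not all of the 9 points is a difference between tests. Simulated Sobel tests reject in about 0.88 of trials at those inputs, so about 6 points come from the approximation in the power formula and about 3 from the test.

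**3. The small/medium case is borderline.** With one path at 0.14, power cannot exceed that of the path alone: Φ(0.14 × 19.698 − 1.960) = Φ(0.798) = 0.788. Reaching 0.80 needs n = ((1.960 + 0.842)/0.14)² ≈ 401. But exactly 2% of variance, with unit residual variance, is a path of √(0.02/0.98) = 0.1429, and Φ(0.1429 × 19.698 − 1.960) = Φ(0.855) = 0.80.

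Covariates matter too. If they explain a share R² of the variance in both models and 0.14 is the unadjusted path, the ceiling is Φ(2.758/√(1−R²) − 1.960): 0.81 at R²=0.05, 0.83 at 0.10, 0.87 at 0.20. These R² values are an assumed range; the plan gives none for the mediation models.

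**4. Why 0.82 is not power for a small effect.** With equal SDs, b1=0.14 implies a correlation of 0.14 and r2 = 0.0196, not 0.3. With that corrected, Sobel power is 0.73 and the planned interval gives 0.79 to 0.80. In addition, with error SD 0.2 the second path explains 0.14² × 0.25 / (0.14² × 0.25 + 0.04) = 0.0049/0.0449 = 11% of outcome variance (8% as a partial share using r2=0.3), not 2%. With an assumed error SD of 0.5, so that both paths are small, Sobel power is about 0.50 and the planned interval about 0.60. The inputs therefore move Sobel power from 0.82 to 0.50, and the change of test then moves it up by about 10 points.

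**The case against.** The strongest reply concerns an inference a reader might draw: that the promise of more than .80 at N=388 fails under the planned interval. The documents do not support that.

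- On the plan's only direct calculation the planned interval gives 0.91, so there the mismatch is conservative.
- For 0.14/0.39 the shortfall is one to two points and disappears if small is taken as exactly 2% of variance. The plan also says that its models will control for demographics and other covariates, and a modest covariate contribution lifts the figure above 0.80.
- The phrase "small to medium effect size of the mediated effect at alpha = 0.05" need not mean one path exactly small. If both paths lie somewhat above small, the planned interval passes 0.80 at about 0.17 each (0.83).

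All of this stands.

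Other replies stand in part. The plan already labels 462 and 377 as bootstrap figures, and 462 exceeds 388, so that citation does not itself claim small/small power at N=388. Only the Sobel sentence does. The plan gives neither the interval level nor an explicit excludes-zero criterion, so the rule used here is the natural reading rather than a written one. The preliminary path regressions do not alter the results: also requiring both paths to be significant left the power unchanged in the cases checked. Mediation is exploratory under Aim 2 and Hypothesis 1 is primary, so the consequence is limited.

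None of this makes a printed figure the power of the planned analysis.

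**Conclusion.** The concern holds in this form: no mediation power or sample size in the plan belongs to the Hypothesis 3 decision rule. The Sobel figure is about 9 points too low at its own inputs (0.82 against 0.91). The bootstrap benchmark for small/small is about 9 points too favourable (.8 against 0.70 to 0.71 at N=462).

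At N=388 the claim of more than .80 is neither established nor refuted. It depends on which effect pair is meant, on how small is rounded and on the covariates, and for 0.14/0.39 the value is about 0.78 to 0.80.

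The sentence giving 0.82 for a small mediated effect does not hold on the plan's own definition of small as 2% of variance, where the planned interval has about 0.58 to 0.60. Blaming the choice of test for that gap would be wrong: the inputs cause it, and the planned interval does better than Sobel's test on the corrected inputs.

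These figures assume flat priors, a two-sided 95% interval and no multiplicity adjustment; the standardised cases also assume no covariates. The primary analysis is not affected.

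**What to change.** In the Sample Size Justification of section 5.6:

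1. Replace the Sobel figure with Monte Carlo power at N=388 for the planned rule, written out: the 95% percentile credibility interval for the product of the two paths excludes zero. State the same rule in the Hypothesis 3 analysis.
2. Use mutually consistent inputs, so that the predictor–mediator correlation follows from the first path and the SDs, and the error SD matches the share of variance called small.
3. Print the effect-size pair, variances and covariate R² beside each power.
4. Say which pair the claim of more than .80 refers to, and keep or revise it according to the simulation. It should be neither deleted nor replaced by a fixed value on the strength of the calculations above.
5. Add that 462 and 377 apply to the bias-corrected bootstrap and do not carry over to the planned interval.

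The cost is a short simulation, a few reworded sentences and possibly a less favourable stated power. Enrolment, conduct and the analysis itself stay as they are.
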